6.3. Methods and timing for assessing, recording, and analysing pharmacokinetic parameters

6.3.1. Collection, treatment and storage of blood samples

Blood sampling will be performed for DF 2755Y concentration measurements at the exact time-points with an authorised time-window described in the table below.

When ECG, vital signs and PK are required at the same time, this specific order will be followed: ECG first, then vital signs and blood sample for PK at the end.

Part A :

Day	Sampling time	Sample N°	Time window(min)
1	T0 (pre-dose)	P00	
	T0h30min	P01	+/-1
	T1h00	P02	+/-3
	T2h	P03	+/-3
	T3h	P04	+/-5
	T4h	P05	+/-5
	T5h	P06	+/-5
	T6h	P07	+/-5
	T7h	P08	+/-5
	T8h	P09	+/-5
	T9h	P10	+/-5
	T10h	P11	+/-5
	T12h	P12	+/-5
	T16h	P13	+/-5
2	T24h	P14	+/-15
	T36h	P15	+/-15
	T40h	P16	+/-15
3	T48h	P17	+/-15
	T60h	P18	+/-15
4	T72h	P19	+/-15

After the determinations of DF 2755Y in plasma samples during cohort 1 and according to results obtained, the blood sampling times and the collection periods could be reviewed to optimize the collection times with respect to the PK profile of DF 2755Y.

Part B :

Day	Sampling time	Sample N°	Time window(min)
1	T0 (pre-dose)	P00	
	T0h30min	P01	+/-1
	T1h00	P02	+/-3
	T2h	P03	+/-3
	T3h	P04	+/-5
	T4h	P05	+/-5
	T5h	P06	+/-5
	T6h	P07	+/-5
	T7h	P08	+/-5
	T8h	P09	+/-5
	T9h	P10	+/-5
	T10h	P11	+/-5
	T12h	P12	+/-5
	T16h	P13	+/-5
2	Pre-dose/T24h D1	P14	+/-15
5	T0 (pre-dose)/ T24h D4	P15	+/-15
	T _{Cmax} ¹	P16	+/-15
	T12h	P17	+/-15
	T _{Cmax} ¹	P18	+/-15
6	Pre-dose/T24h D5	P19	+/-15
10	T0 (pre-dose)/ T24h D9	P20	+/-15
	T _{Cmax} ¹	P21	+/-15
	T12h	P22	+/-15
	T _{Cmax} ¹	P23	+/-15
11	Pre-dose/T24h D10	P24	+/-15

Day	Sampling time	Sample N°	Time window(min)
14	T0 (pre-dose)/ T24h D13	P25	+/-15
	T0h30min	P26	+/-15
	T1h	P27	+/-15
	T2h	P28	+/-15
	T3h	P29	+/-15
	T4h	P30	+/-15
	T5h	P31	+/-15
	T6h	P32	+/-15
	T7h	P33	+/-15
	T8h	P34	+/-15
	T9h	P35	+/-15
	T10h	P36	+/-15
	T12h	P37	+/-15
	T16h	P38	+/-15
15	T24h D14	P39	+/-15
	T36h	P40	+/-15
	T40h	P41	+/-15
16	T48h	P42	+/-15
	T60h	P43	+/-15
17	T72h	P44	+/-15

¹This time (T_{Cmax}) will be determined thanks to part A results.

Blood handling procedures:

A cannula or direct venepuncture will be used to collect blood samples. 6 mL of blood for assay of DF 2755Y and metabolites (if applicable) will be taken into lithium heparin vacutainers. Blood samples will be centrifuged within 15 minutes of collection at 1500 g at 4°C for 10 minutes. Around 3 mL of plasma will be obtained and, immediately after the centrifugation, divided equally into two aliquots. Plasma samples will be stored immediately at approximately -20°C into plus screwed polypropylene tubes.

Blood samples Transport:

Samples will be sent to Dompé farmaceutici S.p.A Bioanalytical Laboratories for analysis. The shipment will be done in a dry ice or under controlled temperature between -15°C and -25°C by a specialized carrier.

Temperatures will be monitored using data logger during all transport. The first set will be sent frozen separately to the second one.

Dompé farmaceutici S.p.A Bioanalytical Laboratories
 [name]
 [name]
 attention to [name].

6.3.2. Collection, treatment and storage of urine samples

Part A:

Urine collection will be performed for DF 2755Y and two metabolites urine concentration measurements, at the following time points:]D-1T-24h – D1T0h(pre-dose)],]D1T0h – D1T6h],]D1T6h – D1T12h],]D1T12h – D2T24h],]D2T24h – D3T48h],]D3T48h – D4T72h].

Part B:

Urine collection will be performed for DF 2755Y and two metabolites urine concentration measurements, at the following time points:]D-1T-24h – D1T0h(pre-dose)],]D1T0h – D1T12h],]D1T12h – D2T24h],]D5T0h – D6T24h],]D10T0h – D11T24h],]D14T0h – D14T12h],]D14T12h – D15T24h],]D15T24h – D16T48h],]D16T48h – D17T72h].

Urine handling procedures:

Urine will be collected for PK analysis from 24 hours before dosing on Day 1 until 72 hours post-dose in Cohorts 1, 2, 3 and 4 (SAD, PART A) and from 24 hours before dosing on Day 1 until 408 h after the first dose in Cohort 5, 6 and 7 (MAD, PART B). The urine collection intervals are detailed above. Subjects will be asked to void their bladders prior to the start of each collection interval and the start and stop time of each collection interval will be recorded in the CRF.

Urine collections for PK analysis will be collected into bottles without preservative. Following completion of each urine collection period, urine pH will be measured and the weight of each collection will be recorded. The collection will be thoroughly mixed and one 5 mL aliquot will be removed from each collection to determine creatinine excretion (Eurofins laboratory). Then two aliquots of 5 mL will be taken for PK analysis and stored at approximately -20°C in stopped polypropylene tubes.

Urine samples Transport:

Samples will be sent to Dompé farmaceutici S.p.A Bioanalytical Laboratories for analysis. The shipment will be done in a dry ice or under controlled temperature between -15°C and -25°C by a specialized carrier. Temperatures will be monitored using data logger during all transport. The first set will be sent frozen separately to the second one.

Dompé farmaceutici S.p.A Bioanalytical Laboratories

[name]

[name]

attention to [name]

6.3.3. Collection, treatment and storage of faeces samples

Part A:

Faeces collection will be performed for DF 2755Y and two metabolites faeces concentration measurements, at the following time points:]D-1T-24h – D1T0h(pre-dose)],]D1T0h – D2T24h],]D2T24h – D3T48h],]D3T48h – D4T72h].

Part B:

Faeces collection will be performed for DF 2755Y and two metabolites faeces concentration measurements, at the following time points:]D-1T-24h – D1T0h(pre-dose)],]D1T0h – D2T24h],]D5T0h – D6T24h],]D10T0h – D11T24h],]D14T0h – D15T24h],]D15T24h – D16T48h],]D16T48h – D17T72h].

Faeces handling procedures:

Faeces will be collected for PK analysis from 24 hours before dosing on Day 1 until 72h post dose in Cohorts 1, 2, 3 and 4 (SAD) and from 24 hours before dosing on Day 1 until 408 h after the first dose in Cohort 5, 6 and 7 (MAD). The faeces collection intervals are detailed above.

After the collection of each faeces samples, the sample will be weighed and homogenized within 30 minute. Two 10 g aliquots of each homogenised sample will be taken. Each 10 g aliquot will be mixed with Phosphate buffered saline (PBS) at PH = 7.4. The faeces/buffer ratio should be 1:2 (e.g., 10 g faeces mixed with 20 mL buffer). The samples (2 aliquots) will be stored at approximately -20°C in stopped polypropylene tubes.

Faeces samples Transport:

Samples will be sent to Dompé farmaceutici S.p.A Bioanalytical Laboratories for analysis. The shipment will be done in dry ice or under controlled temperature between -15°C and -25°C by a specialized carrier. Temperatures will be monitored using data logger during all transport. The first set will be sent frozen separately to the second one.

Dompé farmaceutici S.p.A Bioanalytical Laboratories
[name]
[name]

attention to [name]

6.4. Analytical methods

Plasma, urine and faeces samples will be assayed to determine the concentrations of DF2755Y (bound and unbound plasma sample) according to Dompé farmaceutici S.p.A Bioanalytical Laboratories study plans. The samples will be assayed with validated analytical methods. The metabolic pathway will be also studied to identify the potential metabolites.

7. ASSESSMENT OF PHARMACODYNAMIC

The Assessment of Pharmacodynamic will be performed in Part A (only for leucocyte subsets) starting from the second ascending dose and in Part B of the study.

7.1. Cytokine Inflammation Marker analysis

Inflammation Cytokines:

1. CXCL1 (Gro alfa)
2. CXCL2 (Gro beta) (Biorad)
3. CXCL5 (ENA-78)
4. CXCL6 (GCP-2)
5. CXCL8 (IL-8)

will be analyzed from blood samples.

The method (Elisa) that will be used for the determination of cytokines will be discussed in the final report.

Part B:

Day	Sampling time	Sample N°	Time window(min)
1	T0 (pre-dose)	Il100	NA
5	T0 (pre-dose)	Il101	+/-15
14	T0 (pre-dose)	Il102	+/-15
16	T48h	Il103	+/-15
17	T72h	Il104	+/-15

Blood handling procedures: At each time point indicated in the table, a 10 mL blood sample should be drawn into K2 EDTA tube. This volume is in addition with the one of the assessment of pharmacokinetic described previously. After collection, gently mix the blood by inverting the tube few time for complete mixing with anticoagulant. Store vacutainer tubes upright at 4°C until centrifugation. Blood samples should be centrifuged within four hours of blood collection. Centrifuge blood samples for 15 minutes at 1000 g at 4°C. After centrifugation carefully transfer the plasma layer with an appropriate transfer pipette without disturbing the buffy coat layer to a clean polypropylene tube. To complete remove platelets and precipitates, centrifuge again for 10 min at 10000g at 4°C. Aliquot plasma into 5 pre-labelled polypropylene tubes. Each tube will contain approximately 700 µL of plasma. All sample tubes must be clearly and appropriately labelled. Tubes will be capped immediately from each time point and the plasma will be frozen in an upright position at approximately -80°C for storage.

Blood samples Transport: Samples will be sent to laboratory Hôpital Lyon Sud for analysis of secondary objective. The shipment will be done in a dry ice by a specialized carrier. Temperatures will be monitored using data logger during all transport. Four sets will be sent frozen separately to Hôpital Lyon Sud and one will be kept at EUROFINS OPTIMED.

7.2. Leukocytes subset blood samples

Leukocytes subset: CD11b and CD18 will be analysed on PMN from blood samples.

Part A:

Day	Sampling time	Sample N°	Time window(min)
1	T0 (pre-dose) T_{Cmax} (time will be set after the results of the first dose administered) T_{Cmax} + 3h (time will be determined after the results of the first dose administered) T12h	CD00 – RS00 CD01 – RS01 CD02 – RS02 CD03 – RS03	NA +/-5 +/-5
2	24 h	CD04 – RS04	+/-15
3 or 4	48 h or 72 h (time will be determined after the results of the first dose administered)	CD05 – RS05	+/-15

Part B:

Day	Sampling time	Sample N°	Time window(min)
1	T0 (pre-dose) T_{Cmax}	CD10 – RS10 CD11 – RS11	+/-5
Window from 5 to 7	T0 (pre-dose)/ T_{Cmax}	CD12 – RS12 CD13 – RS13	+/-15 +/-15
14 (Last dose)	T0 T_{Cmax}	CD14 – RS14	+/-15
15	T24h	CD15 – RS15	+/-15

Blood handling procedures:

- CD11b & CD18: at each time point indicated in the table, a 6 mL blood sample should be drawn into a K3 EDTA tube. This volume is in addition with the one of the assessment of pharmacokinetic and for cytokines described previously.

Sample will be treated at Eurofins-Optimed laboratory (detailed will be discuss in the final report) and will be read at immunology laboratory CHU de Grenoble by a flow Cytometer.

Samples Transport: samples will be shipped to Immunology laboratory CHU de Grenoble at 4°C protected from light.

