 - AE/Concomitant medication check (any time);
 - ECG;

D3

- *Before administration*
 - AE/Concomitant medication check (any time);
 - ECG;
- *oral administration in fasting condition.*
 - AE/Concomitant medication check (any time);
 - ECG;

D4

- *Before administration*
 - AE/Concomitant medication check (any time);
 - ECG;
- *oral administration in fasting condition.*
 - AE/Concomitant medication check (any time);

D5

- *Before administration*
 - Physical and medical examination;
 - Laboratory safety (haematology, biochemistry, haemostasis, urinalysis);
 - Vital signs;
 - AE/Concomitant medication check;
 - Blood sampling (PK, cytokine plasma concentration and leukocytes subset);
 - Urine collection;
 - Faeces collection.
- *oral administration in fasting condition.*
 - AE/Concomitant medication check (any time);
 - ECG;
 - Blood sampling (PK and leukocytes subset);
 - Urine collection;
 - Faeces collection.

D6

- *Before administration*
 - AE/Concomitant medication check (any time);
 - ECG;
 - Blood sampling (PK and leukocytes subset if the case)
 - Urine collection;
 - Faeces collection.
- *oral administration in fasting condition.*
 - AE/Concomitant medication check (any time).

- Blood sampling (leukocytes subset if the case)
-

D7

- *Before administration*

- Physical and medical examination;
- Laboratory safety (haematology, biochemistry, haemostasis, urinalysis);
- Vital signs;
- AE/Concomitant medication check.
- Blood sampling (leukocytes subset if the case)
-

- *oral administration in fasting condition.*

- AE/Concomitant medication check (any time);
- ECG.
- Blood sampling (leukocytes subset if the case)

D8

- *Before administration*

- AE/Concomitant medication check;
- ECG.

- *oral administration in fasting condition.*

- AE/Concomitant medication check (any time).

D9

- AE/Concomitant medication check;

D10

- *Before administration*

- Physical and medical examination;
- Laboratory safety (haematology, biochemistry, haemostasis, urinalysis);
- Vital signs;
- AE/Concomitant medication check;
- Blood sampling for PK;
- Urine collection;
- Faeces collection.

- *oral administration in fasting condition.*

- AE/Concomitant medication check (any time);
- ECG;
- Blood sampling for PK;
- Urine collection;
- Faeces collection.

D11

- *Before administration*

- AE/Concomitant medication check (any time);
- ECG;
- Blood sampling for PK;
- Urine collection;
- Faeces collection.

- *oral administration in fasting condition.*

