10.1.1.2. Correlation between pharmacokinetic and pharmacodynamic parameters

The relationship between values of pharmacodynamic parameters time matched with DF2577Y (bound and unbound) plasma concentrations will be first evaluated by visual inspection of graphs relating pharmacodynamic parameters with DF2577Y (bound and unbound) plasma concentrations.

In case of reliable relationships, basic models, such as E_{max} model, will be first developed. Then, the selected models will be optimized by testing covariate such as BMI, age, etc.

Further model development might be done depending on the results of each modelling.

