10.5. Procedure for accounting, for missing, unused, and spurious data

Missing data values will not be replaced.

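### Part B lets the mid-treatment CD11b/CD18 pair be drawn on D5, D6 or D7, but only D5 has a PK sample for both draws: a D6 pair loses its TCmax match, and a D7 pair loses both

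*Protocol*

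**What the plan says.** **Leukocyte sampling.** The Part B table in Protocol section 7.2 gives the day of samples CD12 (pre-dose) and CD13 (TCmax) as "Window from 5 to 7". The footnote to the Part B flow chart repeats the D5 to D7 window for the same two times. I found no rule for choosing the day.

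**PK sampling.** In the Part B table of section 6.3.1, D5 starts with P15, labelled "T0 (pre-dose)/ T24h D4", followed by P16 at TCmax, P17 at 12 h and P18 at the evening TCmax. D6 has one sample, P19, labelled "Pre-dose/T24h D5". The next is P20 on D10, labelled "T0 (pre-dose)/ T24h D9". D7 has none.

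**Visit text.** Section 8.2.2 lists leukocyte sampling together with PK on D5, before and after dosing, without condition. Before the D6 dose the entry is conditional and includes PK: "Blood sampling (PK and leukocytes subset if the case". After the D6 dose, and before and after the D7 dose, it is conditional and has no PK: "Blood sampling (leukocytes subset if the case".

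**Analysis.** Section 10.1.1.2 examines the relationship of "values of pharmacodynamic parameters time matched with DF2577Y (bound and unbound) plasma concentrations", by graph first and then, if a relationship appears, by models such as Emax. Section 10.5 adds: "Missing data values will not be replaced".

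**The concern.** A time-matched analysis needs a measured concentration at the time of each pharmacodynamic value. The window permits days on which the plan draws the leukocyte sample but no PK sample. The protocol provides no substitute: it does not carry the D5 concentration forward, and it does not use a model-predicted one.

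Section 2.2 sets a concentration-response relationship after single and multiple administration as a secondary objective. CD12 and CD13 are the only pre-dose and peak pair with separate sample numbers under repeated dosing, because on D14 section 7.2 puts both times under the single number CD14. On D6 or D7 the draw that loses its match includes the peak, which is an informative point for an Emax model. The loss would be avoidable, since the D5 PK samples are taken anyway.

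**Working it through.** **Inputs**
- PK samples in Part B: P00 to P44 = 45 (section 6.3.1).
- CD11b/CD18 samples in Part B: CD10 to CD15 = 6 (section 7.2).
- Volumes per sample (section 8.2.3): screening 18.7 mL; safety 10.2 mL × 6; PK 6 mL; cytokine 10 mL × 5; CD11b/CD18 6 mL.
- Active subjects in Part B: 9 per dose level × 3 levels = 27 (section 1.6).

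**Step 1: reproduce the plan's blood volume.**
18.7 + 6 × 10.2 + 45 × 6 + 5 × 10 + 6 × 6 = 18.7 + 61.2 + 270 + 50 + 36 = 435.9 mL. This equals the stated Part B total, so the budget holds no unlisted PK sample at D6 TCmax or on D7.

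**Step 2: match each permitted slot to the PK table.**

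| Day of pair | Pre-dose (CD12) | TCmax (CD13) | Matched |
|---|---|---|---|
| D5 | P15 | P16 | 2 of 2 |
| D6 | P19 | none | 1 of 2 |
| D7 | none | none | 0 of 2 |

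**Step 3: size of the loss.** Six draws less the D1 pre-dose draw leaves 5 CD11b/CD18 draws after first dosing.
- All active subjects on D5: 27 × 0 = 0 draws unmatched.
- All on D6: 27 × 1 = 27 draws, 1 of 5 per subject (20%).
- All on D7: 27 × 2 = 54 draws, 2 of 5 per subject (40%).

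These percentages are for CD11b/CD18 only. The five cytokine samples (D1, D5 and D14 pre-dose, D16 at 48 h, D17 at 72 h) all coincide with PK samples. Counting the four cytokine draws after first dosing as well, the D7 case is 2 of 5 + 4 = 9, or 22%.

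**Step 4: cost of adding PK where it is missing.**
- Pair on D6: one more sample, 46 PK samples, 435.9 + 6 = 441.9 mL.
- Pair on D7: two more samples, 47 PK samples, 435.9 + 12 = 447.9 mL.

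**The case against.** The strongest case against runs as follows. D5 lies inside the window and both draws match there. The visit text lists D5 unconditionally and D6 and D7 only conditionally, so D5 looks like the default and the later days a fallback. Section 10.1.1.2 is exploratory and begins with inspection of graphs. Matched CD11b/CD18 draws remain on D1, D14 and D15. The SAP's time-matched list (section 4.3) covers Part A only. Part B cannot start until a substantial amendment is authorised, and its TCmax has still to be set from Part A, so the day could be settled then.

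Most of this stands, and it limits the size of the point. It does not remove the point: the protocol still permits days on which its own planned analysis cannot use the sample, and the pending amendment is an opportunity to correct that.

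Three stronger readings are tempting, and the documents do not support them:
- A reader might infer that any pair drawn after D5 has no PK at all. That is wrong for D6, where P19 is scheduled with the pre-dose leukocyte draw.
- A reader might take 54 lost draws as expected. That requires every active subject in all three cohorts to be drawn on D7, and nothing suggests this is likely.
- A reader might infer that the repeated-dose concentration-response objective fails. Other matched draws remain, and unmatched values can still be described.

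**Conclusion.** The point holds as a conditional defect. Nothing is lost if the pair is drawn on D5. On D6 the TCmax draw, and on D7 both draws, fall outside the time-matched analysis of Protocol section 10.1.1.2. The range is 0 to 54 draws in 27 active subjects, with 27 if all are drawn on D6. The upper limit is a ceiling, not a forecast.

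This rests on three assumptions:
- Time matching means a measured concentration at the same nominal time, which is the plain reading of section 10.1.1.2.
- The other four CD11b/CD18 draws have a PK match, with TCmax on D1 and D14 falling at a scheduled PK time.
- Six draws are taken, as in sections 7.2 and 8.2.3. The D14 visit text in section 8.2.2 does not list the leukocyte draw. If that draw were omitted, the worst-case share would rise to 2 of 4.

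The consequence for Part B rests on the protocol alone, because the SAP specifies time matching only for Part A. The change is worth making because it protects a secondary objective at almost no cost.

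**What to change.** In section 7.2, replace the D5 to D7 window with D5 and state that CD12 is drawn with P15 and CD13 with P16. Amend the flow-chart footnote to agree, and remove the conditional leukocyte entries for D6 and D7 from section 8.2.2. The sample count and the 435.9 mL total do not change, and the pre-dose draw then also coincides with the D5 cytokine sample. The cost is less scheduling flexibility for the cytometry laboratory. The amendment already required before Part B can carry the change.

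If laboratory logistics require D6 or D7, leave P15 to P19 in place and add a 6 mL PK sample at each unmatched leukocyte draw: one for a D6 pair (441.9 mL) or two for a D7 pair (447.9 mL). Sections 6.3.1 and 8.2.3 would need updating. The cost is 6 to 12 mL more blood per subject.

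Moving P15 and P16 to the day of the leukocyte draws is not a good alternative. It would split the D5 PK series from P17 to P19, leave the D5 cytokine sample without a concentration, and separate those PK samples from the D5 to D6 urine and faeces collections. On D6, P15 would also duplicate P19.

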8. ASSESSMENT OF SAFETY

8.1. Specification of safety parameters

8.1.1. Clinical parameters

8.1.1.1. Blood pressure and heart rate

Vital signs consist of systolic (SBP) and diastolic (DBP) blood pressures and heart rate.

The measurements should be made after at least 10 minutes rest in the supine position and after 2 minutes in the standing position, before venepuncture when times of each coincide (except pre-dose).

8.1.1.2. Physical examination

A physical examination including evaluation of main body systems/regions, including: skin and mucous, ears/nose/throat, pulmonary, cardiac, gastro-intestinal and neurological systems.

In case of abnormality, a comment will be recorded in the eCRF.

8.1.1.3. Body weight and height

Measurements of body weight and height (at screening only), will be done during physical examination (when time of body weight measurement coincides with physical examination)

8.1.1.4. Electrocardiogram (ECG)

Twelve-lead ECGs will be recorded after at least 10 minutes in supine position using a Cartouch Cardionics® Device.

ECGs should always be recorded before the PK sampling (if any), except pre-dose.

Each ECG consists of a 10 second recording of the 12 leads simultaneously, leading to a 12-lead ECG (25 mm/s, 10mm/mV) print-out with HR, PR, QRS, QT, QTc automatic correction evaluation, including date, time, number of the subject, signature of the research physician, and at least 3 complexes for each lead. The Investigator medical opinion and automatic values will be recorded in the eCRF. This print-out will be retained at the site level.

8.1.2. Biological parameters

8.1.2.1. Routine laboratory observations

Before the subject is allowed to enter the study a full biological test will be obtained and the absence of clinically significant abnormalities confirmed by the Investigator.

The full biological test comprises:

Haematology: These tests will be performed as follow: Haemoglobin, haematocrit, Red Blood Cells (RBC), White Blood Cells (WBC), differential count, platelet count, Mean Corpuscular Volume (MCV), Mean Corpuscular Haemoglobin (MCH), Mean Corpuscular Hemoglobin Concentration (MCHC).

Hemostasis: PT, aPTT.

Biochemistry: These tests will be performed as follow: Creatinine, fasting blood glucose, total proteins, albumin, globulin (albumin/globulin ratio), total cholesterol, triglycerides, LDH, measured LDL, HDL, electrolytes (sodium, potassium, chloride, calcium, phosphore), uric acid, alanine serine transferase (AST), alanine leucine transferase (ALT), Gamma Glutamyl Transferase (GGT), alkaline phosphatases, urea, creatine phosphokinase (CPK), total and conjugated bilirubin.

